6.9 Study Partner Withdrawal

In the event that a study partner withdraws from the study, the study partner will be asked to complete the Study Partner Withdrawal Form and provide a reason for discontinuation. If a study partner withdraws from the study, the participant (or previous study partner) will be asked to nominate a replacement study partner. If a replacement study partner cannot be identified the subject will complete all end of study assessments as deemed appropriate by the Investigator.

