6.8 Participant Withdrawal

Protocol Version 4, 06 OCT 2021

Confidential

Page 26 of 70

If a participant decides to withdraw from the project, participants are asked to notify a member of the research team. This notice will allow that person or the research supervisor to discuss any health risks or special requirements linked to withdrawing with the participant. Participants will be made aware that the decision to withdraw from the study will not affect their future treatment or relationship with the study doctor.

If a participant withdraws consent during the research project, the study doctor and relevant project team members will not collect additional personal information from the participant. However, personal information already collected will be retained to ensure that the results of the research project can be measured properly and to comply with law. Participants will be made aware that data collected by the Sponsor up to the time the participant withdraws will form part of the research project results. If a participant decides to leave the research project, they will be encouraged to:

- Tell the study doctor
- Return to the study doctor for one more visit

If a participant withdraws consent to participate in this research project, they are entitled to request that all previously retained identifiable biological samples are destroyed, to prevent further analysis according to national provisions.

If participation in the study is stopped earlier than the 104 weeks indicated, the participant will be required to attend a modified schedule of visits. The participant will visit the study centre 4 weeks after they stop taking the study drug.

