- b. If of childbearing potential, must agree not to donate ova, not to attempt to become pregnant and, if engaging in sexual intercourse with a male partner, must agree to the use of acceptable forms of highly effective contraception (refer to Appendix 5) from the time of signing the consent form until at least 30 days after the last dose of the study drug.

12. Male volunteers:

- a. Engaging in any sexual intercourse, including those who are infertile and do not produce sperm (e.g. post-vasectomy), must abstain from unprotected sex until the End of Study visit or equivalent i.e. 4 days after last dose
- b. Must agree to abstain from sperm donation, and if engaging in sexual intercourse with a female of child bearing potential must agree to the use of an acceptable form of highly effective contraception (refer to Appendix 5) from the time of signing the consent form until at least 90 days after the last dose of study drug.
- 13. Estimated life expectancy of at least 2 years, in the opinion of the Investigator.
- 14. Have suitable venous access for blood sampling.
- 15. Be willing and able to comply with all study assessments and adhere to the protocol schedule and restrictions.
- 16. A study partner (partner/spouse/carer) consents to the minimum requirements:
 - a. will attend at least one screening visit
 - b. will be available via phone or in person to provide information to the study as required.

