9.1.1 Investigational Product Administration

The dose and number of 250 mg LorelcoTM or placebo capsules will be administered as described in Table 2. Patients will self-administer investigational product (under the supervision of site staff, or at home) orally, with a full cup (approximately 240 mL) of noncarbonated room temperature water.

Dosing instructions will be detailed in the study Pharmacy Manual and will be provided to the patients at each Investigational Product dispensing.

Orally administered Investigational Products must be swallowed whole and not chewed, divided, dissolved or crushed.

For all drug administrations performed during "at home" periods, participants will self-dose at home unsupervised. Patients will be instructed to return all Webster packs to site staff at each clinic visit for accountability checks. Patients will be instructed not to take the LorelcoTM on clinic visit days until the safety blood samples have been taken.

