11.6 Efficacy Assessments

11.6.1 Screening Assessments

Free and Cued Selective Reminding Test $(FCSRT)^{14}$: The FCSRT assessment will be performed at screening only for eligibility determination. A cueing index of ≤ 0.79 or free recall score of ≤ 17 is required for study entry. The FCSRT is a cued recall test that utilises a controlled encoding technique to ascertainthat impairment in recall and cueing are due to a memory deficit rather than a failure of encoding. Memory impairments due to AD are hippocampal dependent and believed to be characterized by a deficit in recall, often not recovered by cueing. The cueing index measuresthe ability a participant may benefit from being reminded of specific cue words to recall the target word.

Clinical dementia rating scale (CDR) 15 : The CDR provides two scores, a global score (GS) and a sum of boxes (SOB). The GS distinguishes a participant's level of impairment into the following categories: 0 (normal); 0.5 (questionable dementia; 1 (mild dementia); 2 (moderate dementia) and 3 (severe dementia). The SOB is scored from 0-18 with higher scores indicating a greater level of impairment. The scale covers six domains: memory, orientation, judgment and problem solving, community affairs, home and hobbies and personal care. Information to evaluate each rating is obtained through a semi-structured interview with initially the study partner, followed by the participant and takes approximately 40-60 minutesat screening.

Mini Mental State Examination (MMSE)¹⁶: The MMSE is a brief, widely used 30-item assessment of global cognition examining orientation, registration, calculation, recall, attention and language. WORLD backwards will not be used in this protocol. Participants who score <22 at screening will be ineligible for study entry. MMSE will be assessed at screening and EoT (104 weeks).

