11.6.2 Primary Cognitive Assessment

Alzheimer's Disease Assessment Scales-Cognitive Subscale test (ADAS-Cog)¹⁷: The Alzheimer's Disease Assessment Scale-Cognitive Subscale test (ADAS-Cog) is the most widely used test to measure cognition in RCT's for AD. Taking 30 to 40 minutes to administer it is commonly used in clinical trials as it can determine incremental improvements, or decline

Protocol Version 4, 06 OCT 2021

Confidential

Page 39 of 70

in cognitive functioning. The ADAS-Cog12 version consists of the following tasks: Word Recall Task; Following Commands; Constructional Praxis; Delayed Word Recall; Naming Objects and Fingers; Ideational Praxis; Orientation; Word Recognition; Spoken Language; Comprehension and Word Finding Difficulty. Inclusion of the delayed word recall component has shown an increased ability to detect change in the MCI population. Sensitivity of ADAS-Cog is indicated by a scoring differential of approximately six-fold in patients with the earliest manifestation of AD compared to aged-matched health controls. The full suite of ADAS-Cog will be at baseline, 26, 52, 78 and 104 weeks.

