11.6.3 Secondary Cognitive Assessment

Alzheimer's Disease Co-operative Study Mild Cognitive Impairment Activities of Daily Living (ADCS-MCI-ADL24)¹⁸: The ADCS-MCI-ADL24 is a study partner 24-item questionnaire evaluating perceived difficulties with functioning in several activities of daily living across the a variety of domains. The MCI version of the original ADCS-ADL is more sensitive to minor deficits that may be present and provides an overall impairment score, with a higher score indicating a higher level of functioning.

Depression Anxiety Stress Scale (DASS-21)¹⁹: The DASS-21 is a self-report 21-item measure to determine levels of depression, anxiety and stress. It is a shorter version of the original 42-item questionnaire, containing seven questions for each of the domains. Participants are read a statement and asked to rate each statement on a four-point scale as to how much it relates to them. These scores are tallied for each domain and multiplied by two to give a total for depression, anxiety and stress to determine psychological well-being in comparison to normative values. DASS-21 will be administered at day 1/week 1, weeks 26 and 104 (EoS).

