- Haematology, serum chemistry and coagulation tests will be performed (refer to APPENDIX 5). Any new ≥ Grade 3 laboratory abnormality, or change consistent with a possible TEAE (as opposed to disease progression), such as liver function test elevations, electrolyte fluctuation, or hematologic deterioration should be assessed for potential risk to continued dosing. Pre-dose safety laboratory blood samples scheduled for Cycle 1 Day 1 do not need to be repeated if screening blood tests were performed within 4 days prior to study drug administration.
- ¹⁰ ADCS-MCI-ADL24 will be completed by the study partner.
- Standard MRI/PET imaging assessments will be performed during screening and at the EoS visit
- Supply of LorelcoTM or placebo to be provided to the patient for at-home dosing in a Webster pack, with amount provided to last a full cycle.
- Patients to self-administer LorelcoTM or placebo at home, per protocol.
- Adverse events to be monitored throughout the duration of the study.

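### Section 6.9 moves a participant who loses an irreplaceable study partner to end-of-study assessments, so later ADAS-Cog scores are forgone although ADAS-Cog is described without partner input

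*Protocol*

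**What the plan says.** Section 6.9 first asks for a replacement when a study partner withdraws. If none is found: "If a replacement study partner cannot be identified the subject will complete all end of study assessments as deemed appropriate by the Investigator". It does not say when these assessments take place or whether the scheduled visits continue.

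Section 6.8 adds little. Anyone who stops before 104 weeks follows a reduced schedule, of which one visit is specified: "The participant will visit the study centre 4 weeks after they stop taking the study drug".

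The primary outcome is scheduled in section 11.6.2: "The full suite of ADAS-Cog will be at baseline, 26, 52, 78 and 104 weeks". That section lists tasks performed by the participant and names no informant.

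The partner appears in these places:
- **Entry (section 7.2).** The partner attends a screening visit and "will be available via phone or in person to provide information to the study as required".
- **CDR (section 11.6.1).** "Information to evaluate each rating is obtained through a semi-structured interview with initially the study partner". The schedule in Appendix 1 has CDR at screening only.
- **ADCS-MCI-ADL24 (section 11.6.3 and Appendix 1).** "The ADCS-MCI-ADL24 is a study partner 24-item questionnaire evaluating perceived difficulties", and the schedule note confirms: "ADCS-MCI-ADL24 will be completed by the study partner". It is due before baseline and at Weeks 26 and 104.
- **Home dosing.** Section 9.1.1 says "participants will self-dose at home unsupervised"; section 6.1 also allows partner supervision where appropriate.

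**The concern.** The rule lets one person's departure end the collection of another person's primary outcome. The participant may still consent and attend, and nothing in the ADAS-Cog description depends on the partner. The only scheduled scale that cannot be completed is a secondary questionnaire.

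What is at stake is mainly bias. Section 13.6 describes an intention-to-treat analysis of all randomised participants with a random-slope mixed model, and section 13 rules out imputation. Such a model uses the scores a participant already has and handles missingness that those scores explain. ADAS-Cog is measured only every 26 weeks, so a partner may leave because of a decline that no score has yet captured. Those later scores are then missing for a reason the model cannot see. If such decline differs by arm, the treatment contrast is affected. Some precision is lost as well, but that is the smaller matter.

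**Working it through.** **1. What depends on the partner after screening**

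| Assessment | Source of information | Schedule (Appendix 1) |
|---|---|---|
| ADAS-Cog (primary) | Participant | Baseline, Weeks 26, 52, 78, 104 |
| DASS-21 | Participant | Pre-baseline, Weeks 26, 104 |
| PET/MRI | Participant | Screening/pre-baseline, Week 104 |
| ECG, laboratory tests | Participant | Throughout |
| ADCS-MCI-ADL24 (secondary) | Study partner | Pre-baseline, Weeks 26, 104 |

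After baseline, partner loss therefore makes at most two scheduled questionnaires impossible (Weeks 26 and 104).

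**2. ADAS-Cog visits forgone.** There are four post-baseline scores. If the schedule ends with partner loss, the scheduled scores not collected are:
- loss before Week 26: 4
- between Weeks 26 and 52: 3
- between Weeks 52 and 78: 2
- between Weeks 78 and 104: 1

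**3. Is an exit score obtained?** This depends on what end of study means.
- Section 11.6.3 labels Week 104 as EoS for DASS-21. The Appendix 1 imaging note also uses EoS where the schedule marks Week 104. The Week 104 set includes ADAS-Cog, so on this reading one exit score is taken, at the time of partner loss.
- Section 6.1 places the final end-of-study visit 4 weeks after the last dose. In Appendix 1 this is Week 108, where no ADAS-Cog is scheduled.

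Section 6.1 expressly moves imaging to the last visit for those who discontinue. ADAS-Cog has no such provision. On either reading, scores after the exit are not collected.

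**4. The plan's sample size.** Section 13.1 needs 125 per arm and assumes 20% attrition: 125 / 0.80 = 156.25, rounded up to 157 per arm, and 2 × 157 = 314. This reproduces the plan's figure. The allowance is 314 − 250 = 64 participants.

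**5. Illustrative counts.** The partner-loss rates are assumed:
- 3%: 0.03 × 314 = 9.4, and 9.4 / 64 = 15% of the allowance
- 5%: 0.05 × 314 = 15.7, and 15.7 / 64 = 25%
- 8%: 0.08 × 314 = 25.1, and 25.1 / 64 = 39%

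**6. Illustrative power.** The protocol states no alpha; two-sided 0.05 is assumed. Taking the plan's 125 per arm as giving 80% power, power at n per arm is Φ[(1.960 + 0.842) × √(n/125) − 1.960], with n = 157 × (0.80 − extra loss). Treating each affected participant as lost entirely, and beyond the 20%:
- 2% extra: n = 122.5, power 79%
- 5% extra: n = 117.8, power 78%
- 10% extra: n = 109.9, power 75%

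This overstates the effect, because earlier scores stay in the model.

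**The case against.** The strongest reply is that section 6.9 never says the participant is discontinued. It gives no time for the assessments and leaves them to the investigator's judgement, and partner loss is not a listed withdrawal reason in section 6.2, which does however have an investigator catch-all. A reader might infer that the protocol mandates discontinuation; the text does not go that far. This part of the objection stands. It leaves a rule that sites can apply differently and that nowhere provides for the remaining ADAS-Cog visits.

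A reader might also infer that the primary outcome is discarded for these participants. The documents do not support that. Earlier scores enter the mixed model, and an exit score is taken if end of study means the Week 104 set.

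Third, a two-year trial in Alzheimer's disease has good reason to want an informant, and section 7.2 makes partner availability an entry condition. That is a fair reason to seek a replacement. It does not explain why a test given to the participant should stop.

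Fourth, the size is unproven. No partner-loss rate is given, some of this loss may already lie within the 20% allowance, and a participant without a partner may be unable to attend anyway, so it cannot be claimed that every such loss is avoidable. The link between partner loss and decline is also plausible rather than documented. All of this stands and limits the claim to a risk of bias.

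**Conclusion.** The point holds in a limited form. Read plainly, section 6.9 forgoes later ADAS-Cog scores in participants who lose an irreplaceable partner, for a reason the ADAS-Cog description does not require. This departs from intention-to-treat follow-up. It can bias the comparison if partner loss is related to decline not yet observed; neither the presence nor the direction of such bias can be established from the protocol.

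Per participant affected after Week 26, up to three of four post-baseline scores are at stake, with possibly one exit score obtained. Across the trial, any count is an assumption: about 9 to 25 participants at 3% to 8%. The likely effect on power is small, and it is zero relative to plan if these losses are already within the 20%. The amendment is worth making because it is cheap and missed visits cannot be recovered later. It is not a flaw that invalidates the design.

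**What to change.** Amend section 6.9 so that a consenting participant without a replacement partner stays on the scheduled ADAS-Cog, DASS-21, imaging, ECG and laboratory assessments to Week 104, with only ADCS-MCI-ADL24 recorded as missing. State which visit end of study refers to. Record the date of any partner change, so that ADCS-MCI-ADL24 scores can be read with the informant known.

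Whether partner loss affects study treatment is not addressed here; sections 6.2, 6.8 and 6.9 should be reconciled on that point.

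The cost is one paragraph and one eCRF field. The downside is less informant information on adverse events and adherence for a few participants.

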6.10 Missed Doses

In the event that a participant misses a dose of the medication, the participant will be instructed that the capsule should be taken as soon as possible. If more than two hours have passed since the scheduled medication time, the participant will be instructed to skip this dose of the medication and resume taking the medication at the next scheduled time. Participants will also be instructed not to double-dose if they miss a scheduled medication. It will be made clear to the participant that taking a double-dose of the medication may increase the risk of adverse side effects.

.

Protocol Version 4, 06 OCT 2021

Confidential

Page 27 of 70

7 PATIENT SELECTION

7.1 Number of Patients

Estimated sample sizes are calculated for the two primary outcome measurements: ADAS-Cog and GM atrophy (hippocampal). In order to ensure that the study has sufficient power to detect differences in both of the primary outcomes, the sample size chosen is the maximum of that calculated for each primary outcome.

The primary analysis was an intention-to-treat analysis and included all randomized participants. Data will be analysed using both Generalised Estimating Equations (GEE) and Bayesian Analysis.

The analysis of primary endpoints will use linear mixed-effects models, with random slopes and intercepts. For the ADAS-Cog, using mixed model analysis published estimates from the ADNI cohort17 suggest a sample size of 125 AD participants per trial arm (total N = 250) will be required for power at 0.8 to detect a drug effect of 25% over two years and assuming a decline from baseline of 1.10 standardised units on the composite (SD change = 0.83).

For the MRI markers, Ledig et al. $(2018)^{24}$ reported the sample sizes required for a 25% intervention reduction over two years based on 322 patients with AD (with 117 followed for 24 months) and a reduction of 10.2% (6.2) for hippocampus 18. Sample size calculations based on hippocampal volume suggest that 93 subjects per treatment arm are required (total N = 186).

Assuming a 20% attrition rate, a sample of 314 subjects will be recruited for the Cognitive study, and 233 subjects will be randomly chosen for the Imaging study.

7.2 Inclusion Criteria

Patients must satisfy all of the following criteria to be enrolled in the study:

- 1. Must have given written informed consent before any study-related activities are carried out and must be able to understand the full nature and purpose of the trial, including possible risks and adverse effects.
- 2. Adult males and females, 18 to 84 (inclusive) at screening.
- 3. Diagnosis of Alzheimer's Disease confirmed by:
 - a. A positive amyloid biomarker (PET scan) indicative of AD pathology,
 - b. Mini-mental-state examination (MMSE) score of 22 or greater,
 - c. Free and cued selective reminding test (FCSRT) cueing index of 0.79 or less OR free recall score ≤17
 - d. Clinical Dementia Rating (CDR) global score of 0.5 or 1.0.
- 4. Able to take oral medications and willing to record daily adherence to the study drug.
- 5. QT interval corrected using the Fridericia method (QTcF) ≤ 450 msec for males and ≤ 460 msec for females at screening and on Day 1, prior to dose administration (the mean of two measurements will be used to determine eligibility).
- 6. Evidence of adequate hepatic function at screening, as defined by the following:
 - a. Aspartate aminotransferase (AST) and alanine aminotransferase (ALT) $\leq 2.5 \times$ upper limit

Protocol Version 4, 06 OCT 2021

Confidential

Page 28 of 70

of normal (ULN) (\leq 5 × ULN if liver metastases are present); and

- b. Total bilirubin ≤1.5 × ULN (< 2.0 x ULN for subjects with liver metastases or documented Gilbert's syndrome).
- 7. Evidence of adequate renal function, as defined by a calculated creatinine clearance ≥50 mL/min using the Cockcroft-Gault equation or 24-hour urine collection with plasma and urine creatinine concentrations respectively.
- 8. Adequate coagulation laboratory assessments (i.e. results within normal ranges, per local laboratory definition) at screening.
- 9. Lipids (total cholesterol, HDL and LDL) must be within < 1.5 x the upper limit of normal for the local laboratory reference range at the screening visit.
- 10. FBC must be within < 1.5 x the upper limit of normal for the local laboratory reference range at the screening visit.

11. Female volunteers:

- a. Must be of non-childbearing potential (i.e., surgically sterilised [hysterectomy, bilateral salpingectomy, bilateral oophorectomy at least 6 weeks before the screening visit]) or postmenopausal (where postmenopausal is defined as no menses for 12 months without an alternative medical cause, or
- b. If of childbearing potential, must agree not to donate ova, not to attempt to become pregnant and, if engaging in sexual intercourse with a male partner, must agree to the use of acceptable forms of highly effective contraception (refer to Appendix 5) from the time of signing the consent form until at least 30 days after the last dose of the study drug.

12. Male volunteers:

- a. Engaging in any sexual intercourse, including those who are infertile and do not produce sperm (e.g. post-vasectomy), must abstain from unprotected sex until the End of Study visit or equivalent i.e. 4 days after last dose
- b. Must agree to abstain from sperm donation, and if engaging in sexual intercourse with a female of child bearing potential must agree to the use of an acceptable form of highly effective contraception (refer to Appendix 5) from the time of signing the consent form until at least 90 days after the last dose of study drug.
- 13. Estimated life expectancy of at least 2 years, in the opinion of the Investigator.
- 14. Have suitable venous access for blood sampling.
- 15. Be willing and able to comply with all study assessments and adhere to the protocol schedule and restrictions.
- 16. A study partner (partner/spouse/carer) consents to the minimum requirements:
 - a. will attend at least one screening visit
 - b. will be available via phone or in person to provide information to the study as required.

